10.0 TREATMENT/INTERVENTION PLAN

10.1 Administration

Within 4 weeks of screening date, eligible patients will receive combination pembrolizumab and olaparib as maintenance therapy until clinical or radiographic progression or discontinuation due to -limiting toxicity. If a patient requires discontinuation of either olaparib or pembrolizumab for reasons of toxicity and if in the opinion of the treating MD the patient is continuing to derive benefit, the patient is able to continue on study. Additionally, in the absence of unacceptable toxicity, participants who meet criteria for disease progression per RECIST 1.1 while receiving treatment will be permitted to continue treatment, if in the opinion of the treating MD the patient is continuing to derive benefit from the treatment. iRECIST will be used to evaluate the objective response rate and the co-primary endpoint of overall response rate will be assessed by RECIST v1.1. (Section 12.0 CRITERIA FOR REMOVAL FROM STUDY).

The POLAR treatment will be administered to subjects as outlined in Figure 1 - Schematic treatment and biospecimen collection schedule. Approximately within 4 weeks of screen visit, patient will get baseline biopsy and will start the first dose pembrolizumab 200 mg IV every 3 weeks and olaparib 300 mg twice daily orally. After the first 6 months (9 cycles), on C10D1 Pembrolizumab 400 mg IV every 6 week plus olaparib 300 mg twice a day orally will be continued. Per treating investigator's discretion, patients may remain at Pembrolizumab 200 mg IV every 3 weeks after the first 9 cycles. Additionally, to accomodate patients traveling far distances, if, per treating investigator, after the first or second imaging, there are no toxicities, patient's dosing of Pembrolizumab may change to 400 mg IV every 6 weeks. All cycles will be 21 days (3 weeks) in length. Subjects will be monitored for toxicity every three weeks for the first 9 cycles, and every six weeks thereafter, unless clinically indicated to be monitored every 3 weeks.

Table 2. Trial treatment (POLAR)

Drug	Dose	Dose Frequency	Route of Administration	Treatment Period	Use
Pembrolizumab	200 mg	Q3W	IV infusion	Day 1 of each 3- week cycle for cycle 1-9	experimental
Pembrolizumab	400mg	Q6W	IV infusion	Day 1 of every even cycle beginning with Cycle 10	experimental
Olaparib	300 mg (two 150 mg)	BID	Orally	Daily continuously	experimental

The following parameters must be acceptable prior to initiation of protocol treatment:

- Absolute neutrophil count (ANC) ≥1500/µL
- Hemoglobin ≥9.0 g/dL or ≥5.6 mmol/La
- Platelets ≥100 000/µL
- Total bilirubin ≤ 2 x ULN
- AST (SGOT) and ALT (SGPT) ≤2.5 × ULN (≤5 × ULN for if liver metastases)
- Creatinine ≤2 x ULN

10.2 Timing of Dose Administration

Trial treatment should be administered on Day 1 of each cycle after all procedures or assessments have been completed as detailed on the Trial Flow Chart (Section 6.0). Trial treatment may be administered up to 3 days before or after the scheduled Day 1 of each cycle due to administrative reasons. On the day of the treatment, participants can receive oral olaparib AM dose at the clinic visit followed by pembrolizumab.

All trial treatments will be administered on an outpatient basis.

Pembrolizumab will be infused per MSK guidelines. Pembrolizumab 200 mg will be administered as a 30-minute IV infusion every 3 week. After the first 6 months (9 cycles), on C10D1 Pembrolizumab 400 mg IV every 6 week plus olaparib 300 mg twice a day orally will be continued. Pembrolizumab 200 mg IV every 3 weeks may continue after Cycle 9, and Pembrolizumab 400 mg IV every 6 weeks may begin earlier than Cycle 9 per treating physician's discretion. Given the variability of infusion pumps a window of -5 minutes and +10 minutes is permitted (i.e., infusion time is 30 minutes: -5 min/+10 min).

8

POLAR: a phase 2 trial for pembrolizumab and olaparib maintenance for metastatic PDAC and HRD and/or Exceptional Response to Platinum – Ver. 5/3/2020

10.3 Dose Modification and Toxicity Management for Immune-Related AEs Associated with Pembrolizumab

AEs associated with pembrolizumab exposure may represent an immunologic etiology. These immune-related AEs (irAEs) may occur shortly after the first dose or several months after the last dose of pembrolizumab treatment and may affect more than on body system simultaneously. Therefore, early recognition and initiation of treatment is critical to reduce complications. Based on existing clinical study data, most irAEs were reversible and could be managed with interruptions of pembrolizumab, administration of corticosteroids and/or other supportive care. For suspected irAEs, ensure adequate evaluation to confirm etiology or exclude other causes. Additional procedures or tests such as bronchoscopy, endoscopy, skin biopsy may be included as part of the evaluation. Based on the severity of irAEs, withhold or permanently discontinue pembrolizumab and administer corticosteroids. Dose modification and toxicity management guidelines for irAEs associated with pembrolizumab are provided in Table 3.

Table 3 Dose modification and toxicity management guidelines for immune-related AEs associated with pembrolizumab

General instructions:

- 1. Severe and life-threatening irAEs should be treated with IV corticosteroids followed by oral steroids. Other immunosuppressive treatment should begin if the irAEs are not controlled by corticosteroids.
- 2. Pembrolizumab must be permanently discontinued if the irAE does not resolve or the corticosteroid dose is not ≤10 mg/day within 12 weeks of the last pembrolizumab treatment.
- 3. The corticosteroid taper should begin when the irAE is ≤ Grade 1 and continue at least 4 weeks.
- 4. If pembrolizumab has been withheld, pembrolizumab may resume after the irAE decreased to ≤ Grade 1 after corticosteroid taper.

irAEs	Toxicity grade (CTCAE V5.0)	Action with pembrolizumab	Corticosteroid and/or other therapies	Monitoring and follow-up
Pneumonitis	Grade 2 Grade 3 or 4, or recurrent Grade 2	Permanently discontinue	Administer corticosteroids (initial dose of 1 - 2 mg/kg prednisone or equivalent) followed by taper Add prophylactic antibiotics for opportunistic infections	Monitor participants for signs and symptoms of pneumonitis Evaluate participants with suspected pneumonitis with radiographic imaging and initiate corticosteroid treatment
Diarrhea / Colitis	Grade 2 or 3 Grade 4 or recurrent Grade 3	Permanently discontinue	Administer corticosteroids (initial dose of 1 - 2 mg/kg prednisone or equivalent) followed by taper	 Monitor participants for signs and symptoms of enterocolitis (i.e., diarrhea, abdominal pain, blood or mucus in stool with or without fever) and of bowel perforation (i.e., peritoneal signs and ileus) Participants with ≥Grade 2 diarrhea suspecting colitis should consider GI consultation and performing endoscopy to rule out colitis

				Participants with diarrhea/colitis should be advised to drink liberal quantities of clear fluids. If sufficient oral fluid intake is not feasible, fluid and electrolytes should be substituted via IV infusion
AST or ALT elevation or	Grade 2 ª	Withhold	Administer corticosteroids (initial dose of 0.5 - 1 mg/kg prednisone or equivalent) followed by taper	Monitor with liver function tests (consider weekly or more frequently until liver enzyme value returned to baseline or is
Increased Bilirubin	Grade 3 ^b or 4 ^c	Permanently discontinue	Administer corticosteroids (initial dose of 1 - 2 mg/kg prednisone or equivalent) followed by taper	stable)
Type 1 diabetes mellitus (T1DM) or Hyperglycemia	New onset T1DM or Grade 3 or 4 hyperglycemia associated with evidence of β-cell failure	Withhold ^d	 Initiate insulin replacement therapy for participants with T1DM Administer antihyperglycemic in participants with hyperglycemia 	Monitor participants for hyperglycemia or other signs and symptoms of diabetes
Hypophysitis	Grade 2 Grade 3 or 4	Withhold or permanently discontinue d	Administer corticosteroids and initiate hormonal replacements as clinically	Monitor for signs and symptoms of hypophysitis (including hypopituitarism and adrenal
	Grade 2	Continue	indicated Treat with non-selective betablockers (e.g.,	 insufficiency) Monitor for signs and symptoms of thyroid disorders
Hyperthyroidism	Grade 3 or 4	Withhold or permanently discontinue d	propranolol) or thionamides as appropriate	แบบเป็น นเรอเนยเร

Hypothyroidism	Grade 2, 3, or 4	Continue	Initiate thyroid replacement hormones (e.g., levothyroxine or liothyronine) per standard of care	Monitor for signs and symptoms of thyroid disorders
Nephritis and renal dysfunction: grading according to increased creatinine or acute kidney injury	Grade 2 Grade 3 or 4	Withhold Permanently discontinue	Administer corticosteroids (prednisone 1 – 2 mg/kg or equivalent) followed by taper	Monitor changes of renal function
Myocarditis	Grade 1 or 2 Grade 3 or 4	Withhold Permanently discontinue	Based on severity of AE administer corticosteroids	Ensure adequate evaluation to confirm etiology and/or exclude other causes
All Other immune-related AEs	Intolerable/persistent Grade 2 Grade 3 Grade 4 or recurrent Grade 3	Withhold or discontinue based on the event e. Permanently discontinue	Based on severity of AE administer corticosteroids	Ensure adequate evaluation to confirm etiology or exclude other causes

^a AST/ALT: >3.0 - 5.0 x ULN if baseline normal; >3.0 - 5.0 x baseline, if baseline abnormal; bilirubin:>1.5 - 3.0 x ULN if baseline normal; >1.5 - 3.0 x baseline if baseline abnormal

Pembrolizumab may cause severe or life-threatening infusion-reactions including severe hypersensitivity or anaphylaxis. Signs and symptoms usually develop during or shortly after drug infusion and generally resolve completely within 24 hours of completion of infusion. Dose modification and toxicity management guidelines on pembrolizumab associated infusion reaction are provided in Table 4. If the patient has grade 3 LFT's not attibruted to drug, patient may continue treatment, per treating MD's discretion.

Table 4. Pembrolizumab infusion reaction dose modification and treatment guidelines

^b AST/ALT: >5.0 to 20.0 x ULN, if baseline normal; >5.0 - 20.0 x baseline, if baseline abnormal; bilirubin:>3.0 - 10.0 x ULN if baseline normal; >3.0 - 10.0 x baseline if baseline abnormal

^c AST/ALT: >20.0 x ULN, if baseline normal; >20.0 x baseline, if baseline abnormal; bilirubin: >10.0 x ULN if baseline normal; >10.0 x baseline if baseline abnormal

^d The decision to withhold or permanently discontinue pembrolizumab is at the discretion of the investigator or treating physician. For participants with Grade 3 or 4 immune-related endocrinopathy where withhold of pembrolizumab is required, pembrolizumab may be resumed when AE resolves to ≤ Grade 2 and is controlled with hormonal replacement therapy or achieved metabolic control (in case of T1DM)

^e Events that require discontinuation include but are not limited to: Guillain-Barre Syndrome, encephalitis, Stevens-Johnson Syndrome and toxic epidermal necrolysis.

NCI CTCAE Grade

Treatment

Premedication at

	Treatment	Premedication at
		Subsequent Dosing
Grade 1	Increase monitoring of vital signs as medically	None
Mild reaction; infusion	indicated until the participant is deemed	
interruption not	medically stable in the opinion of the investigator.	
indicated; intervention		
not indicated		
Grade 2	Stop Infusion.	Participant may be
Requires therapy or	Additional appropriate medical therapy may	premedicated 1.5h (± 30
infusion interruption but	include but is not limited to:	minutes) prior to infusion of
responds promptly to	IV fluids	with:
symptomatic treatment	Antihistamines	Diphenhydramine 50 mg po
(e.g., antihistamines,	NSAIDs	(or equivalent dose of
NSAIDs, narcotics, IV	Acetaminophen	antihistamine).
fluids); prophylactic	Narcotics	Acetaminophen 500-1000 mg
medications indicated	Increase monitoring of vital signs as medically	po (or equivalent dose of
for ≤24 hrs	indicated until the participant is deemed	analgesic).
	medically stable in the opinion of the investigator.	
	If symptoms resolve within 1 hour of stopping	
	drug infusion, the infusion may be restarted at	
	50% of the original infusion rate (e.g. from 100	
	mL/hr to 50 mL/hr). Otherwise dosing will be	
	held until symptoms resolve and the participant	
	should be premedicated for the next scheduled	
	dose.	
	Participants who develop Grade 2 toxicity	
	despite adequate premedication should be	
	permanently discontinued from further study	
	drug intervention	
Grades 3 or 4	Stop Infusion.	No subsequent dosing
Grade 3:	Additional appropriate medical therapy may	-
Prolonged (i.e., not	include but is not limited to:	
rapidly responsive to	Epinephrine**	
10-1-10-1		
symptomatic	IV fluids	
	IV fluids Antihistamines	
symptomatic		
symptomatic medication and/or brief	Antihistamines	
symptomatic medication and/or brief interruption of infusion);	Antihistamines NSAIDs	
symptomatic medication and/or brief interruption of infusion); recurrence of	Antihistamines NSAIDs Acetaminophen	
symptomatic medication and/or brief interruption of infusion); recurrence of symptoms following	Antihistamines NSAIDs Acetaminophen Narcotics	
symptomatic medication and/or brief interruption of infusion); recurrence of symptoms following initial improvement;	Antihistamines NSAIDs Acetaminophen Narcotics Oxygen	
symptomatic medication and/or brief interruption of infusion); recurrence of symptoms following initial improvement; hospitalization	Antihistamines NSAIDs Acetaminophen Narcotics Oxygen Pressors	
symptomatic medication and/or brief interruption of infusion); recurrence of symptoms following initial improvement; hospitalization indicated for other	Antihistamines NSAIDs Acetaminophen Narcotics Oxygen Pressors Corticosteroids	
symptomatic medication and/or brief interruption of infusion); recurrence of symptoms following initial improvement; hospitalization indicated for other clinical sequelae (e.g.,	Antihistamines NSAIDs Acetaminophen Narcotics Oxygen Pressors Corticosteroids Increase monitoring of vital signs as medically	
symptomatic medication and/or brief interruption of infusion); recurrence of symptoms following initial improvement; hospitalization indicated for other clinical sequelae (e.g., renal impairment,	Antihistamines NSAIDs Acetaminophen Narcotics Oxygen Pressors Corticosteroids Increase monitoring of vital signs as medically indicated until the participant is deemed	
symptomatic medication and/or brief interruption of infusion); recurrence of symptoms following initial improvement; hospitalization indicated for other clinical sequelae (e.g., renal impairment, pulmonary infiltrates)	Antihistamines NSAIDs Acetaminophen Narcotics Oxygen Pressors Corticosteroids Increase monitoring of vital signs as medically indicated until the participant is deemed medically stable in the opinion of the investigator.	

Life-threatening;	Participant is permanently discontinued from			
pressor or ventilatory	further study drug intervention.			
support indicated				
Appropriate resuscitation equipment should be available at the bedside and a physician readily available during the				
period of drug administration.				
For further information, please refer to the Common Terminology Criteria for Adverse Events v5.0 (CTCAE) at				
http://ctep.cancer.gov				

Other allowed dose interruption for pembrolizumab

Pembrolizumab may be interrupted for situations other than treatment-related AEs such as medical/surgical events or logistical reasons not related to study therapy. Participants should be placed back on study therapy within 3 weeks of the scheduled interruption, unless otherwise discussed with the Sponsor. The reason for interruption should be documented in the patient's study record.

10.4 Rescue Medications & Supportive Care for AEs Associated with Pembroizumab

Participants should receive appropriate supportive care measures as deemed necessary by the treating investigator. Suggested supportive care measures for the management of AEs with potential immunologic etiology are outlined along with the dose modification guidelines in Section 5.2.2, [Table 3]. Where appropriate, these guidelines include the use of oral or IV treatment with corticosteroids, as well as additional anti-inflammatory agents if symptoms do not improve with administration of corticosteroids. Note that several courses of steroid tapering may be necessary as symptoms may worsen when the steroid dose is decreased. For each disorder, attempts should be made to rule out other causes such as metastatic disease or bacterial or viral infection, which might require additional supportive care. The treatment guidelines are intended to be applied when the Investigator determines the events to be related to pembrolizumab.

It may be necessary to perform conditional procedures such as bronchoscopy, endoscopy, or skin photography as part of evaluation of the event.

10.7 Dose modification and toxicity management for AEs associated with olaparib

Dose Reductions

For guidance on dose reductions when concomitant strong or moderate CYP3A inhibitors cannot be avoided see below Table 6 and Table 7.

When dose reduction is necessary patients will take one 150 mg tablet and one 100 mg tablet twice daily or two x 100 mg tablet twice daily, or one 150 mg tablet twice daily or one 100 mg tablet twice daily. If further reduction is required, treating investigators should follow the SOC use for Olaparib.

In case a dose reduction is necessary, the Study treatment will be administered as follows:

Table 5. Dose reductions for study treatment to manage adverse events

Initial Dose	Following re-challenge post interruption: Dose reduction 1	Dose reduction 2*
300 mg twice daily	250 mg twice daily	200 mg twice daily
(Two 150 mg tablets)	(150 mg tablet and 100 mg tablet)	(Two 100 mg tablets)

^{*}If further reduction is required, treating investigators should follow the SOC use for Olaparib.

Table 6. Dose reduction for study treatment if patient develops moderate renal impairment

Initial Dose	Moderate renal impairment (calculated creatinine clearance by Cockcroft -Gault equation or based on a 24-hour urine test between 31 and 50 ml/min): Dose reduction	
300 mg twice daily	CrCl 51 to 80 mL/minute: No dosage adjustment necessary.	
	CrCl 31 to 50 mL/minute: Reduce dose to 200 mg twice daily.	
	CrCl ≤30 mL/minute: There are no dosage adjustments provided in the manufacturer's labeling (has not been studied).	
	End-stage renal disease: There are no dosage adjustments provided in the manufacturer's labeling (has not been studied).	

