10.6 Management of adverse events for AEs associated with olaparib

Any toxicity observed during the course of the study could be managed by interruption of the dose of study treatment or dose reductions. Repeat dose interruptions are allowed as required, for a maximum of 4 weeks on each occasion. If the interruption is any longer, the study team must be informed. Study treatment can be dose reduced to 250 mg twice daily as a first step and to 200 mg twice daily as a second step. If further reduction is required, treating invesigators should follow the SOC use for Olaparib. If patient is clinically benefiting from prior POLAR treatment, patient can continue to receive pembrolizumab alone or olaparib alone depending on the specific toxicity related to one of these agents. Once dose is reduced, escalation is not permitted (except following concomitant treatment with CYP3A4 inhibitors – see Section 6.5

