10.6.2 Management of non-hematological toxicity associated with olaparib

Repeat dose interruptions are allowed as required, for a maximum of 4 weeks on each occasion. If the interruption is any longer than this the study monitor must be informed. Where toxicity reoccurs following re-challenge with study treatment, and where further dose interruptions are considered inadequate for management of toxicity, then the patient should be considered for dose reduction or must permanently discontinue study treatment.

Study treatment can be dose reduced to 250 mg twice daily as a first step and to 200 mg twice daily as a second step. If further reduction is required, treating investigators should follow the SOC use for Olaparib. Treatment must be interrupted if any NCI-CTCAE grade 3 or 4 adverse event occurs which the investigator considers to be related to administration of study treatment.

Page | 37

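### Section 10.7 names four reduced olaparib levels before referring to SOC use, Table 5 and Sections 10.6 and 10.6.2 name two, and nothing says which cause the two lower levels serve

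*Protocol*

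**What the plan says.** Protocol Section 10.7 covers dose modification for adverse events associated with olaparib. Its first sentence under Dose Reductions sends the reader to Tables 6 and 7 for reductions when strong or moderate CYP3A inhibitors cannot be avoided. The next sentence is general: "When dose reduction is necessary patients will take one 150 mg tablet and one 100 mg tablet twice daily", then "or two x 100 mg tablet twice daily", then "or one 150 mg tablet twice daily or one 100 mg tablet twice daily". After that comes "If further reduction is required, treating investigators should follow the SOC use for Olaparib".

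Directly below stands "Table 5. Dose reductions for study treatment to manage adverse events". It shows the 300 mg start, a first reduction to 250 mg and a second to 200 mg, all twice daily. The footnote to the second reduction repeats the SOC sentence.

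Section 10.6 states: "Study treatment can be dose reduced to 250 mg twice daily as a first step and to 200 mg twice daily as a second step". It then makes the same SOC referral. It also bars escalation after a reduction, except following CYP3A4 inhibitors, for which it points to Section 6.5.

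Section 10.6.2 (non-hematological toxicity) repeats the two steps and the SOC referral. For toxicity that returns on re-challenge, where more interruptions are judged inadequate, it says "then the patient should be considered for dose reduction or must permanently discontinue study treatment".

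Table 7 (anemia) and Table 8 (neutropenia, leukopenia, thrombocytopenia) name 250 mg and then 200 mg twice daily. Neither carries the SOC sentence.

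**The concern.** The same SOC instruction takes over at different doses depending on which paragraph is read, and two of the four levels in the Section 10.7 text appear nowhere else in the reduction rules. An investigator whose patient has toxicity at 200 mg twice daily finds named lower levels in the text. Table 5 gives only a referral to SOC use, which the protocol does not define.

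The cause of a reduction has a second consequence. Under Section 10.6 a reduced dose may go back up only after a CYP3A4 inhibitor. Whether 150 or 100 mg twice daily is an adverse-event level or an interaction level therefore also decides whether the dose may return. These rules set what patients receive, and protocol monitoring and any summary of exposure need one rule to check against.

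**Working it through.** No sample size, power or error rate enters here, so the check is a comparison of the text with simple tablet arithmetic.

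**Tablet arithmetic for the Section 10.7 sentence (each dose twice daily, start 300 mg)**
- 150 + 100 = 250 mg; 250/300 = 83%
- 2 × 100 = 200 mg; 200/300 = 67%
- 1 × 150 = 150 mg; 150/300 = 50%
- 1 × 100 = 100 mg; 100/300 = 33%

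**Side by side**

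| Place | Stated cause | Named reduced levels (mg twice daily) | SOC referral comes after |
|---|---|---|---|
| 10.7, text | none in the sentence; section heading is adverse events | 250, 200, 150, 100 | 100 |
| 10.7, Table 5 | adverse events | 250, 200 | 200 |
| 10.6 | any toxicity | 250, 200 | 200 |
| 10.6.2 | non-hematological toxicity | 250, 200 | 200 |
| 10.6.1.1, Table 7 | anemia | 250, 200 | no referral given |
| 10.6.1.2, Table 8 | neutropenia, leukopenia, thrombocytopenia | 250, 200 | no referral given |

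The named levels differ (four against two). So does the dose at which the SOC referral begins: 100 mg in the text, 200 mg in Table 5 and Sections 10.6 and 10.6.2. Both differences already exist within Section 10.7.

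**Can the cause of the 150 and 100 mg levels be traced?**
1. *CYP3A inhibitors.* The preceding sentence concerns them, so this is the natural candidate. Its pointer fails: Table 6 is about moderate renal impairment and Table 7 about anemia. The Section 10.6 pointer fails too: Section 6 contains only 6.1 (inclusion) and 6.2 (exclusion). Section 6.2 restricts CYP3A inhibitors at entry and gives a washout, but no olaparib dose. The table of contents numbers the anemia table 8 and the neutropenia table 9, one higher than in the body. That would fit a table having been dropped or renumbered, but does not prove it.
2. *Renal impairment.* Table 6 and Section 10.6.6 name 200 mg twice daily as the reduced dose. Neither names 150 or 100 mg.
3. *Adverse events.* The section heading points this way, but every list expressly tied to adverse events (Table 5, Section 10.6, Section 10.6.2, Tables 7 and 8) ends its named steps at 200 mg.

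None of the three routes settles what the two lower levels are for.

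**The case against.** The strongest reply is that nothing here is a contradiction between two adverse-event ladders. The four-level sentence names no cause and directly follows the CYP3A sentence. Section 10.6 treats CYP3A4 reductions as a separate case, and Table 5 is the list expressly titled for adverse events. On that reading 150 and 100 mg belong to drug interactions and the adverse-event steps agree everywhere. This is plausible, and the documents do not exclude it. But the sentence sits under an adverse-event heading, is worded for any necessary reduction, and ends in the same SOC referral as Table 5. The guidance that would confirm the CYP3A reading is not where either pointer leads. The ambiguity therefore stands.

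A reader might go further in three ways that the documents do not support:
- *That 200 mg twice daily is a floor in Table 5 and Section 10.6.* It is not. Only the named steps end there. Section 10.6 continues that investigators "should follow the SOC use for Olaparib. If patient is clinically benefiting from prior POLAR treatment", and Table 5 and Section 10.6.2 likewise allow further reduction under SOC use. A lower dose is not shown to breach them.
- *That a patient at 200 mg has three written outcomes: reduce, follow SOC, or stop.* The discontinuation wording in Section 10.6.2 concerns recurrent non-hematological toxicity and is tied to no dose level. Offering reduction or discontinuation as alternatives does not conflict with Table 5.
- *That the Cohort A 6-month PFS or ORR counts are affected.* No such effect is shown. Section 10.6.5 requires all reductions, interruptions and their reasons to be recorded in the eCRF, so the exposure actually given can be described.

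The SOC referral itself appears in Section 10.7, Table 5 and Sections 10.6 and 10.6.2 and looks deliberate. The inconsistency lies in where it begins, and its presence is no fault.

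**Conclusion.** The point holds as an inconsistency in the dose-reduction rules. The Section 10.7 text names four reduced levels, down to 33% of the starting dose, before referring to SOC use. Table 5 and Sections 10.6 and 10.6.2 name two, down to 67%, and make the referral there. Tables 7 and 8 agree with the two-level version. These figures compare named levels, not permitted doses. The purpose of the 150 and 100 mg levels cannot be established from the document, and it matters because Section 10.6 makes re-escalation depend on it.

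The conclusion rests on the wording alone and assumes that no CYP3A dosing guidance exists elsewhere in the protocol as available. How many patients would be affected is unknown. No consequence for sample size, power, type I error or the primary endpoint counts is claimed, and no view is taken on which levels are right.

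**What to change.** Reconcile the Section 10.7 text, Table 5, Sections 10.6 and 10.6.2, and Tables 7 and 8, so that:
- the named levels for adverse events are the same in every place;
- the SOC referral begins at the same point wherever it appears;
- the cause that the 150 mg and 100 mg twice-daily levels serve is stated;
- the CYP3A cross-references (Tables 6 and 7 in Section 10.7, Section 6.5 in Section 10.6) lead to the guidance they promise.

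The sponsor decides the levels, and whether and where the SOC rule applies. The cost is protocol wording in the next amendment; the design and the analysis do not change.
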